1.2 Study Schema

Figure 1 Study Design Schema

[figure not shown]

★ Dose Escalation Committee (DEC) Meeting

★ Interim Analysis (IA)

[figure not shown]
A: active; P: placebo; L: low-dose ASP0598; H: high-dose ASP0598

Figure 2 Study Flow Chart – SAD

[figure not shown]
CBC: complete blood count; PK: pharmacokinetic; SAD: Single Ascending Dose

Figure 3 Study Flow Chart – Single Dose Expansion

[figure not shown]
CBC: complete blood count

Figure 4 Study Flow Chart – MAD

CBC: complete blood count; MAD: Multiple Ascending Dose; PK: pharmacokinetic

[figure not shown]
Figure 5 Study Flow Chart – Multiple Dose Expansion

* Additional treatments on Day 15 and 29 will be conducted if the subject has not achieved complete closure of TMP.

CBC: complete blood count

[figure not shown]
Figure 6 Otology Examination and PK Blood Draw Flow Chart – Single Dose

Through Day 29 (SAD) or through Day 57 (Single Dose Expansion)

Day 57 (SAD), Day 85 (Single Dose Expansion) or EOS

[figure not shown]
Footnotes appeared on next page

EOS: end of study; PK: pharmacokinetic; PTA: Pure Tone Audiometry; SAD: single ascending dose; TM: tympanic membrane; VAS: Tinnitus Visual Analog Scale

- a. After ASP0598 Otic Solution or placebo administration, subjects will be required to remain on their side with the treated ear facing up for at least 15 minutes. Please see the Pharmacy Manual, Section 9.4: Dose Administration for detailed instructions.
- b. Day 1, imaging picture will be taken pre-dose, immediately after, 30 (± 5) minutes and 60 (± 5) minutes after ASP0598 Otic Solution or placebo administration into the affected ear.
- c. PK blood samples will be collected on Day 1 at pre-dose (-15) minutes and at the following post-dose time points: 30 (± 5) minutes and 60 (± 5) minutes. PK blood sampling will be performed only in SAD after ASP0598 Otic Solution or placebo administration into the affected ear.
- d. Skin local reaction at the ASP0598 Otic Solution/placebo application site will be evaluated by Modified Brighton Grading Scheme (Appendix [12.9](#)) at all visits.
- e. Ear cleaning will not be conducted between Days 2 – 29 (SAD) or Days 2 – 57 for (single dose expansion), unless it is absolutely necessary. Investigators will not clean the treated ear by suctioning unless subjects experience uncomfortable ear discharge).
- f. At Day 57 (SAD) or Day 85 (single dose expansion) and/or EOS, the whole TM should be visible before taking imaging picture. If the whole TM is not visible, the investigator should clean the ear canal.

Figure 7 Otology Examination and PK Blood Draw Flow Chart – Multiple Dose

Days 1, 15, and 29 – Dosing

Through Day 57 except for Days 15 and 29 (MAD) or Through – Day 85 (Multiple Dose Expansion)

Microscopic ear examination^{e, f} / Imaging picture
PTA (Bone at 1, 2, 4 kHz), TVAS

Day 85 (MAD) and Day 113 (Multiple Dose Expansion) or EOS

Microscopic ear examination ^{e, g} / Imaging picture
PTA (Bone + Air), Tympanometry, TVAS

Footnotes appear on next page

EOS: end of study; MAD: multiple ascending dose; PK: pharmacokinetic; PTA: Pure Tone Audiometry; TM: tympanic membrane; TVAS: Tinnitus Visual Analog Scale.

- a. Days 15 and 29, PTA will be conducted only for bone conduction hearing at 1, 2, 4 kHz and Tympanometry will not be conducted.
- b. After ASP0598 Otic Solution or placebo administration, subjects will be required to remain on their side with the treated ear facing up for at least 15 minutes. Please see the Pharmacy Manual, Section 9.4: Dose Administration for detailed instructions.
- c. Days 1, 15, and 29, imaging picture will be taken pre-dose, immediately after, 30 (± 5) minutes and 60 (± 5) minutes after ASP0598 Otic Solution or placebo administration into the affected ear.
- d. Day 1 and Day 29, PK blood draw will be performed pre-dose (-15) minutes, 30 (± 5) minutes and 60 (± 5) minutes after ASP0598 Otic Solution or placebo administration into the affected ear. PK sampling will be performed only during MAD.
- e. Skin local reaction at the ASP0598 Otic Solution/placebo application site will be evaluated by Modified Brighton Grading Scheme (Appendix [12.9](#)) at all visits.
- f. Ear cleaning will not be conducted between Days 2 – 57 (MAD) or Days 2 – 85 for (multiple dose expansion), unless it is absolutely necessary. Investigators will not clean the treated ear by suctioning unless subjects experience uncomfortable ear discharge).
- g. At Day 85 (MAD) or Day 113 (multiple dose expansion) and/or EOS, the whole TM should be visible before taking imaging picture. If the whole TM is not visible, the investigator should clean the ear canal.
- h. For multiple dose expansion, ASP0598 Otic Solution or placebo administration on Day 15 and Day 29 will be conducted in the case that the TMP closure is not confirmed. If the treatment is not conducted on these visits, imaging pictures and Microscopic ear examination for skin local reaction after the drug administration will be skipped.

1.3 Schedule of Assessments

Table 2 Schedule of Assessments – SAD

| | Day | Screening | Randomization | Observation | | | | |
|---|----------------|-------------------|----------------|----------------|----------------|----------------|----------------|------------------------------|
| | | Day -28 to Day -1 | Day 1 | Day 2 | Day 8 | Day 15 | Day 29 | Day 57 Last Visit/ EOS |
| Week | | | | | Week 1 | Week 2 | Week 4 | Week 8 |
| Visit Windows | | | | + 1 day | +/- 3 days | +/- 3 days | +/- 3 days | +/- 3 days |
| Visit number | 1 | 2 | 3 | 4 | 5 | 6 | 7 | |
| Study Procedures | | | | | | | | |
| Informed Consent | X | | | | | | | |
| Verify Inclusion/Exclusion | X | X | | | | | | |
| Medical History/Disease History/Demographics | X | X | | | | | | |
| Physical Exam including Height and Weight | X | | | | | | | |
| Vital Signs ^a | X | X | X | X | X | X | X | |
| Prior/Concomitant Medications ^b | X | X | X | X | X | X | X | |
| Adverse Events Assessment ^c | X | X | X | X | X | X | X | |
| Study Treatment Administration | | | | | | | | |
| ASP0598 or placebo | | X ^d | | | | | | |
| Otology Examinations | | | | | | | | |
| Microscopic Ear Examination | X ^e | X ^f | X ^g | X ⁱ |
| Modified Brighton Grading Scheme Evaluation | | X ^f | X | X | X | X | X | X |
| Imaging picture of tympanic membrane by endoscope | X ^e | X ^h | X | X | X | X | X | X |
| Bone conduction by Pure Tone Audiometry (PTA) | X ^e | X | X ^j | X |
| Air conduction by PTA | X ^e | X | | | | | | X |
| Tympanometry | X ^e | X | | | | | | X |
| Tinnitus Visual Analog Scale (TVAS) | X | X | X | X | X | X | X | X |

Table continued on next page

| Day | Screening | Randomization | Observation | | | | |
|----------------------------------|-------------------|----------------|-------------|------------|------------|------------|------------------------------|
| | Day -28 to Day -1 | Day 1 | Day 2 | Day 8 | Day 15 | Day 29 | Day 57 Last Visit/ EOS |
| Week | | | | Week 1 | Week 2 | Week 4 | Week 8 |
| Visit Windows | | | + 1 day | +/- 3 days | +/- 3 days | +/- 3 days | +/- 3 days |
| Visit number | 1 | 2 | 3 | 4 | 5 | 6 | 7 |
| Blood Collection | | | | | | | |
| Serum Chemistries | X | | | | | | |
| CBC with Differential | X | | | | | | |
| Pregnancy Test ^k | X | X | | | | | X |
| Pharmacokinetic Sample | | X ¹ | X | | | | |
| Blood Sample for Future Analysis | | X | | | | X | |
| Urine Collection | | | | | | | |
| Urinalysis | X | | | | | | |

AE: adverse event; CBC: complete blood count; EOS: end of study; SAD: single ascending dose; TM: tympanic membrane

- a. Vital Signs include blood pressure, body temperature, and heart rate.
- b. Includes all medications taken within 28 days prior to ASP0598 Otic Solution or placebo administration at Day 1.
- c. AEs will be collected from the time of informed consent through Day 57 or EOS. Any AEs ongoing at Day 57 or EOS Visit must be followed until resolution or investigator determines the event to be stable. AEs should be assessed at least monthly.
- d. ASP0598 Otic Solution or placebo will be applied onto the remaining tympanic membrane under a microscope with a 22-gauge blunt needle. After ASP0598 Otic Solution or placebo administration, subjects will be required to remain on their side with the treated ear facing up for at least 15 minutes. Please see the Pharmacy Manual, Section 9.4: Dose Administration for detailed instructions.
- e. Otology examinations will be performed for both ears at the screening visit.
- f. Microscopic Ear examination will be performed prior to and 60 (± 5) minutes after ASP0598 Otic Solution/placebo administration. Skin local reaction at the application site will be evaluated by Modified Brighton Grading Scheme (Appendix 12.9) at 60 (± 5) minutes after ASP0598 Otic Solution/placebo administration.
- g. Ear cleaning will not be conducted between Days 2 – 29, unless it is absolutely necessary. Investigators will not clean the treated ear by suctioning unless subject's experience uncomfortable ear discharge.
- h. At Day 1, imaging pictures will be taken at the following time points: pre-dose, immediately after, 30 (± 5) minutes, and 60 (± 5) minutes after the ASP0598 Otic Solution or placebo administration.
- i. At Day 57 or EOS, the whole TM should be visible before taking imaging picture. If the whole TM is not visible, the investigator should clean the ear canal.
- j. Bone conduction testing at Day 2, 8, 15, 29 will be tested only at 1, 2 and 4 kHz (ototoxicity assessment).
- k. Urine or serum pregnancy test will be performed in women of childbearing potential.
- l. Day 1, PK blood draw will be performed at the following time points: pre-dose (-15) minutes, 30 (± 5) minutes and 60 (± 5) minutes after ASP0598 Otic Solution or placebo administration into the affected ear.

Table 3 Schedule of Assessments – Single Dose Expansion

| | Screening | Randomization | Observation | | | Day 85 Last Visit/ EOS |
|---|----------------|-------------------|----------------|----------------|----------------|------------------------------|
| | Day | Day -28 to Day -1 | Day 1 | Day 15 | Day 29 | |
| Week | | | Week 2 | Week 4 | Week 8 | Week 12 |
| Visit Windows | | | +/- 3 days | +/- 3 days | +/- 3 days | +/- 3 days |
| Visit number | 1 | 2 | 3 | 4 | 5 | 6 |
| Study Procedures | | | | | | |
| Informed Consent | X | | | | | |
| Verify Inclusion/Exclusion | X | X | | | | |
| Medical History/Disease History/Demographics | X | X | | | | |
| Physical Exam including Height and Weight | X | | | | | |
| Vital Signs ^a | X | X | X | X | X | X |
| Prior/Concomitant Medications ^b | X | X | X | X | X | X |
| Adverse Events Assessment ^c | X | X | X | X | X | X |
| Study Treatment Administration | | | | | | |
| ASP0598 or placebo | | X ^d | | | | |
| Otology Examinations | | | | | | |
| Microscopic Ear Examination | X ^e | X ^f | X ^g | X ^g | X ^g | X ⁱ |
| Modified Brighton Grading Scheme Evaluation | | X ^f | X | X | X | X |
| Imaging picture of tympanic membrane by endoscope | X ^e | X ^h | X | X | X | X |
| Bone conduction by Pure Tone Audiometry (PTA) | X ^e | X | X ^j | X ^j | X ^j | X |
| Air conduction by PTA | X ^e | X | | | | X |
| Tympanometry | X ^e | X | | | | X |
| Tinnitus Visual Analog Scale (TVAS) | X | X | X | X | X | X |

Table continued on next page

| | Screening | Randomization | Observation | | | |
|----------------------------------|------------------|----------------------|--------------------|------------|------------|------------|
| | Day | Day -28 to Day -1 | Day 1 | Day 15 | Day 29 | Day 57 |
| Week | | | Week 2 | Week 4 | Week 8 | Week 12 |
| Visit Windows | | | +/- 3 days | +/- 3 days | +/- 3 days | +/- 3 days |
| Visit number | 1 | 2 | 3 | 4 | 5 | 6 |
| Blood Collection | | | | | | |
| Serum Chemistries | X | | | | | |
| CBC with Differential | X | | | | | |
| Pregnancy Test ^k | X | X | | | X | X |
| Blood Sample for Future Analysis | | X | | X | | |
| Urine Collection | | | | | | |
| Urinalysis | X | | | | | |

AE: adverse event; CBC: complete blood count; EOS: end of study; TM: tympanic membrane

- a. Vital Signs include blood pressure, body temperature, and heart rate.
- b. Includes all medications taken within 28 days prior to ASP0598 Otic Solution or placebo administration at Day 1.
- c. AEs will be collected from the time of informed consent through Day 57 or EOS. Any AEs ongoing at Day 85 or EOS Visit must be followed until resolution or investigator determines the event to be stable. AEs should be assessed at least monthly.
- d. ASP0598 Otic Solution or placebo will be applied onto the remaining tympanic membrane under a microscope with a 22-gauge blunt needle. After ASP0598 Otic Solution or placebo administration, subjects will be required to remain on their side with the treated ear facing up for at least 15 minutes. Please see the Pharmacy Manual, Section 9.4: Dose Administration for detailed instructions.
- e. Otology examinations will be performed for both ears at the screening visit.
- f. Microscopic Ear examination will be performed prior to and 60 (± 5) minutes after ASP0598 Otic Solution/placebo administration. Skin local reaction at the application site will be evaluated by Modified Brighton Grading Scheme (Appendix 12.9) at 60 (± 5) minutes after ASP0598 Otic Solution/placebo administration.
- g. Ear cleaning will not be conducted between Days 2 – 57, unless it is absolutely necessary. Investigators will not clean the treated ear by suctioning unless subjects experience uncomfortable ear discharge.
- h. At Day 1, imaging pictures will be taken at the following time points: pre-dose, immediately after, 30 (± 5) minutes, and 60 (± 5) minutes after the ASP0598 Otic Solution or placebo administration.
- i. At Day 85 or EOS, the whole TM should be visible before taking imaging picture. If the whole TM is not visible, the investigator should clean the ear canal.
- j. Bone conduction testing at Day 15, 29, and 57 will be tested only at 1, 2 and 4 kHz (ototoxicity assessment).
- k. Urine or serum pregnancy test will be performed in women of childbearing potential.

Table 4 Schedule of Assessments – MAD

| | Day | Screening | Randomization | Observation | | | | | | | |
|---|------|--------------------|----------------|----------------|-------------------|----------------|-------------------|----------------|----------------|------------------------------|--|
| | | Day – 28 to Day -1 | Day 1 | Day 8 | Day 15 | Day 22 | Day 29 | Day 36 | Day 57 | Day 85 Last Visit/ EOS | |
| Visit Windows | Week | | | Week 1 | Week 2 | Week 3 | Week 4 | Week 5 | Week 8 | Week 12 | |
| Visit number | | 1 | 2 | 3 | 4 | 5 | 6 | 7 | 8 | 9 | |
| Study Procedures | | | | | | | | | | | |
| Informed Consent | | X | | | | | | | | | |
| Verify Inclusion/Exclusion | | X | X | | | | | | | | |
| Medical History/Disease History/Demographics | | X | X | | | | | | | | |
| Physical Exam including Height and Weight | | X | | | | | | | | | |
| Vital Signs ^a | | X | X | X | X | X | X | X | X | X | |
| Prior/Concomitant Medications ^b | | X | X | X | X | X | X | X | X | X | |
| Adverse Events Assessment ^c | | X | X | X | X | X | X | X | X | X | |
| Study Treatment Administration | | | | | | | | | | | |
| ASP0598 or placebo ^d | | | X | | X | | X | | | | |
| Otology Examinations | | | | | | | | | | | |
| Microscopic Ear Examination | | X ^e | X ^f | X ^g | X ^{f, g} | X ^g | X ^{f, g} | X ^g | X ^g | X ⁱ | |
| Modified Brighton Grading Scheme Evaluation | | | X ^f | X | X ^f | X | X ^f | X | X | X | |
| Imaging picture of tympanic membrane by endoscope | | X ^e | X ^h | X | X ^h | X | X ^h | X | X | X | |
| Bone conduction by Pure Tone Audiometry (PTA) | | X ^e | X | X ^j | X ^j | X ^j | X ^j | X ^j | X ^j | X | |
| Air conduction by PTA | | X ^e | X | | | | | | | X | |
| Tympanometry | | X ^e | X | | | | | | | X | |
| Tinnitus Visual Analog Scale (TVAS) | | X | X | X | X | X | X | X | X | X | |

Table continued on next page

| | | Screening | Randomization | Observation | | | | | | |
|-----------------------------|------|--------------------|----------------------|--------------------|------------|------------|------------|------------|------------|------------------------------|
| | Day | Day – 28 to Day -1 | Day 1 | Day 8 | Day 15 | Day 22 | Day 29 | Day 36 | Day 57 | Day 85 Last Visit/ EOS |
| | Week | | | Week 1 | Week 2 | Week 3 | Week 4 | Week 5 | Week 8 | Week 12 |
| Visit Windows | | | | +/- 3 days | +/- 3 days | +/- 3 days | +/- 3 days | +/- 3 days | +/- 3 days | +/- 3 days |
| Visit number | | 1 | 2 | 3 | 4 | 5 | 6 | 7 | 8 | 9 |
| Blood Collection | | | | | | | | | | |
| Serum Chemistries | | X | | | | | | | | |
| CBC with Differential | | X | | | | | | | | |
| Pregnancy Test ^k | | X | X | | | | | | X | X |
| Pharmacokinetic Sample | | | X ^l | | | | X | | | |
| Sample for Future Analysis | | | X | | | | | | X | |
| Urine Collection | | | | | | | | | | |
| Urinalysis | | X | | | | | | | | |

AE: adverse event; CBC: complete blood count; EOS: end of study; TM: tympanic membrane

- a. Vital Signs include blood pressure, body temperature, and heart rate.
- b. Includes all medications taken within 28 days prior to ASP0598 Otic Solution or placebo administration at Day 1.
- c. AEs will be collected from the time of informed consent through Day 85 or EOS. Any AEs ongoing at Day 85 or EOS Visit must be followed until resolution or investigator determines the event to be stable. AEs should be assessed at least monthly.
- d. ASP0598 Otic Solution or placebo will be applied onto the remaining tympanic membrane under a microscope with a 22-gauge blunt needle. After ASP0598 Otic Solution or placebo administration, subjects will be required to remain on their side with the treated ear facing up for at least 15 minutes. Please see the Pharmacy Manual, Section 9.4: Dose Administration for detailed instructions.
- e. Otology examinations will be performed for both ears at the screening visit.
- f. Days 1, 15 and 29, microscopic ear examination will be performed prior to and 60 (± 5) minutes after ASP0598 Otic Solution/placebo administration. Skin local reaction at the application site will be evaluated by Modified Brighton Grading Scheme (Appendix 12.9) at 60 (± 5) minutes after ASP0598 Otic Solution/placebo administration.
- g. Ear cleaning will not be conducted between Days 2 – 57, unless it is absolutely necessary. Investigators will not clean the treated ear by suctioning unless subjects experience uncomfortable ear discharge).
- h. At Days 1, 15, and 29, imaging pictures will be taken at the following time points: pre-dose, immediately after, 30 (± 5) minutes, and 60 (± 5) minutes after the ASP0598 Otic Solution or placebo administration.
- i. At Day 85 and/or EOS, the whole TM should be visible before taking imaging picture. If the whole TM is not visible, the investigator should clean the ear canal.
- j. Bone conduction testing at Day 8, 15, 22, 29, 36 and 57 will be tested only at 1, 2 and 4 kHz (ototoxicity assessment).
- k. Urine or serum pregnancy test will be performed in women of childbearing potential.
- l. Day 1 and Day 29, PK blood draw will be performed at the following time points: pre-dose (-15) minutes, 30 (± 5) minutes and 60 (± 5) minutes after ASP0598 Otic Solution or placebo administration into the affected ear.

Table 5 Schedule of Assessments – Multiple Dose Expansion

| | Day | Screening | Randomization | Observation | | | | | |
|---|------|--------------------|----------------|------------------|------------------|----------------|----------------|----------------|-------------------------------|
| | | Day – 28 to Day -1 | Day 1 | Day 15 | Day 29 | Day 43 | Day 57 | Day 85 | Day 113 Last Visit/ EOS |
| Visit Windows | Week | | | Week 2 | Week 4 | Week 6 | Week 8 | Week 12 | Week 16 |
| Visit number | | 1 | 2 | 3 | 4 | 5 | 6 | 7 | 8 |
| Study Procedures | | | | | | | | | |
| Informed Consent | | X | | | | | | | |
| Verify Inclusion/Exclusion | | X | X | | | | | | |
| Medical History/Disease History/Demographics | | X | X | | | | | | |
| Physical Exam including Height and Weight | | X | | | | | | | |
| Vital Signs ^a | | X | X | X | X | X | X | X | X |
| Prior/Concomitant Medications ^b | | X | X | X | X | X | X | X | X |
| Adverse Events Assessment ^c | | X | X | X | X | X | X | X | X |
| Study Treatment Administration | | | | | | | | | |
| ASP0598 or placebo ^d | | | X | X ¹ | X ¹ | | | | |
| Otology Examination | | | | | | | | | |
| Microscopic Ear Examination | | X ^e | X ^f | X ^{f,g} | X ^{f,g} | X ^g | X ^g | X ^g | X ⁱ |
| Modified Brighton Grading Scheme Evaluation | | | X ^f | X ^f | X ^f | X | X | X | X |
| Imaging picture of tympanic membrane by endoscope | | X ^e | X ^h | X ^h | X ^h | X | X | X | X |
| Bone conduction by Pure Tone Audiometry (PTA) | | X ^e | X | X ^j | X ^j | X ^j | X ^j | X ^j | X |
| Air conduction by PTA | | X ^e | X | | | | | X | X |
| Tympanometry | | X ^e | X | | | | | X | X |
| Tinnitus Visual Analog Scale (TVAS) | | X | X | X | X | X | X | X | X |
| Blood Collection | | | | | | | | | |
| Serum Chemistries | | X | | | | | | | |
| CBC with Differential | | X | | | | | | | |
| Pregnancy Test ^k | | X | X | | | | X | | X |
| Sample for Future Analysis | | | X | | | | X | | |
| Urine Collection | | | | | | | | | |
| Urinalysis | | X | | | | | | | |

Footnotes appear on next page

AE: adverse event; CBC: complete blood count; EOS: end of study; TM: tympanic membrane; TMP: tympanic membrane perforation

- a. Vital Signs include blood pressure, body temperature, and heart rate.
- b. Includes all medications taken within 28 days prior to ASP0598 Otic Solution or placebo administration at Day 1.
- c. AEs will be collected from the time of informed consent through Day 113 or EOS. Any AEs ongoing at Day 113 or EOS Visit must be followed until resolution or investigator determines the event to be stable. AEs should be assessed at least monthly.
- d. ASP0598 Otic Solution or placebo will be applied onto the remaining tympanic membrane under a microscope with a 22-gauge blunt needle. After ASP0598 Otic Solution or placebo administration, subjects will be required to remain on their side with the treated ear facing up for at least 15 minutes. Please see the Pharmacy Manual, Section 9.4: Dose Administration for detailed instructions.
- e. Otology examinations will be performed for both ears at the screening visit.
- f. Microscopic Ear examination will be performed prior to and 60 (± 5) minutes after ASP0598 Otic Solution/placebo administration. Skin local reaction at the application site will be evaluated by Modified Brighton Grading Scheme (Appendix 12.9) at 60 (± 5) minutes after ASP0598 Otic Solution/placebo administration.
- g. Ear cleaning will not be conducted between Days 2 – 85, unless it is absolutely necessary. Investigators will not clean the treated ear by suctioning unless subjects experience uncomfortable ear discharge).
- h. At Days 1, 15, and 29, imaging pictures will be taken at the following time points: pre-dose, immediately after, 30 (± 5) minutes, and 60 (± 5) minutes after the ASP0598 Otic Solution or placebo administration.
- i. At Day 85 (SAD) or Day 113 (single dose expansion) and/or EOS, the whole TM should be visible before taking imaging picture. If the whole TM is not visible, the investigator should clean the ear canal.
- j. Bone conduction testing at Day 15, 29, 43, 57, and 85 will be tested only at 1, 2 and 4 kHz (ototoxicity assessment).
- k. Urine or serum pregnancy test will be performed in women of childbearing potential.
- l. ASP0598 Otic Solution or placebo administration on Day 15 and Day 29 will be conducted in the case that the TMP closure is not confirmed.

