dose concentration of MAD will be 5.0 µg/mL, and another dose concentration up to a maximum feasible dose concentration of 15 µg/mL will be considered.

The first interim analysis will be conducted after completion of the last SAD cohort. Data will be summarized for all time points available. The second interim analysis will be conducted after completion of the last MAD cohort.

The Data Monitoring Committee (DMC) will review the data and make the final decision to open single and/or multiple dose expansion. The DMC operation, roles and responsibilities will be described in the DMC Charter.

Subjects may be replaced at the discretion of the sponsor. If replaced, the replacement subject will be given the same treatment group the original subject's randomized treatment group.

Dose Expansion

The decision to open single and/or multiple dose expansion will be made based on the safety and efficacy results of the interim analyses after completion of SAD and after completion of MAD by the DMC per the charter. Once the decision to open single and/or multiple dose expansion is made, the number of treatment groups (2 or 3 treatment groups including 1 or 2 active treatment groups and 1 placebo group) and the dose for ASP0598 Otic Solution will be selected based on the safety and efficacy result of the interim analyses. All analyses will be described in the Interim Analysis Plan (IAP).

Up to 39 subjects will be randomized to single dose and/or multiple dose expansion. Based on the interim analysis results:

- If 3 treatment groups are selected, approximately 39 subjects will be randomized in a 1:1:1 ratio of high dose ASP0598 Otic Solution, low dose ASP0598 Otic Solution, or placebo (13 subjects in each treatment group).
- If 2 treatment groups are selected, approximately 26 subjects will be randomized in a 1:1 ratio of high dose ASP0598 Otic Solution or placebo (13 subjects in each treatment group).

Stratification at the time of randomization will be based on the % size of the TMP at the screening visit and subjects will be balanced equally between the treatment groups. Dose expansion will assess safety and efficacy of ASP0598 Otic Solution.

Single Dose Expansion

After randomization on Day 1, subjects will receive ASP0598 Otic Solution or placebo administration into the affected ear at the investigative site. Subjects will return to the investigative site for assessments on Days 15, 29, 57, and 85 (EOS).

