7.3.1 Time Period for Collecting Adverse Event and Serious Adverse Event Information

In order to identify any events that may be associated with study procedures and could lead to a change in the conduct of the study, Astellas collects AEs even if the subject has not received IP. AE collection begins after the signing of the ICF and will be collected until 14 days after the last study visit or when the subject is determined to be a screen failure.

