9.5.1 Adverse Events

AEs will be coded using MedDRA.

A TEAE is defined as an AE observed after starting administration of the study drug through EOS visit. A drug-related TEAE is defined as any TEAE with a causal relationship assessed as “yes” by the investigator.

An overview of TEAEs and Death by treatment group will be presented. In addition, the following summaries will be presented by SOC and PT:

- TEAEs by treatment group
- Drug-related TEAEs by treatment group
- Serious TEAEs by treatment group
- Drug-related serious TEAEs by treatment group

An overview of TEAEs of special interest by treatment group will be presented. The following summaries will be presented by SOC and PT:

- TEAEs of special interest by treatment group
- Serious TEAEs of special interest by treatment group

Details about selection of AEs of special interest will be provided in the SAP.

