6.9 Additional Conventions

6.9.1 Analysis Windows for Safety Variables

For the assessments where the summaries and/or analyses are presented by analysis visit during study period, post baseline values will not contribute to the safety analyses:

- SAD: if the study day of the value is > minimum(study day of end of study visit, 57) + 7 days.
- Single dose expansion and MAD: if the study day of the value is > minimum(study day of end of study visit, 85) + 7 days.
- Multiple dose expansion: if the study day of the value is > minimum (study day of end of study visit, 113) + 7 days.

For the assessments where the summaries and/or analyses are not presented by analysis visit during study period (AEs, previous and concomitant medications and modified brighton grading scheme), end day of end of study visit is defined as follows:

- SAD: minimum(study day of end of study visit, 57) + 7 days.
- Single dose expansion and MAD: minimum(study day of end of study visit, 85) + 7 days.
- Multiple dose expansion: minimum (study day of end of study visit, 113) + 7 days.

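### Single dose expansion: the footnote on adverse event collection names Day 57 as an end day, although the part ends at the Day 85 visit

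*Protocol*

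**What the plan says.** Footnote c to the adverse event row of Protocol Table 3 (single dose expansion) reads: "AEs will be collected from the time of informed consent through Day 57 or EOS". Its next sentence uses a different day: "Any AEs ongoing at Day 85 or EOS Visit must be followed until resolution or investigator determines the event to be stable". Table 14, the crisis version of the same schedule in Section 12.11, carries both sentences.

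Protocol Section 4.1 places the visits of this part on Days 15, 29, 57 and 85 and labels Day 85 as EOS. The adverse event row is marked at all six visits in both tables, including the Week 12 visit.

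Three other provisions set an end for adverse events:

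- Protocol Section 7.3.1, on collection: events "will be collected until 14 days after the last study visit".
- Protocol Section 9.5.1, on what counts as treatment-emergent: "A TEAE is defined as an AE observed after starting administration of the study drug through EOS visit".
- SAP Section 6.9.1, on the last day counted: "Single dose expansion and MAD: minimum(study day of end of study visit, 85) + 7 days".

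**The concern.** The collection sentence in Tables 3 and 14 is identical to the one in the SAD schedule, where Day 57 is the final visit. In single dose expansion Day 57 is the Week 8 visit, and the two alternatives in the phrase are four weeks apart.

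Treatment-emergent adverse events and adverse events of special interest are primary endpoints. If some sites took Day 57 as the end of collection, late events there would go unrecorded while the analysis window stayed open, and an event that was not collected would look the same as one that did not occur. The stretch at risk, Days 58 to 85, is exactly the follow-up that single dose expansion adds to SAD. Investigators are blinded, so such a loss would not be expected to favour one arm systematically. The result would be an undercount of late events, uneven between sites.

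**Working it through.** The documents give no figure of their own for this point, so the check compares the passages and then does the day arithmetic.

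**1. Is Day 57 the final day of this part?** The schedules follow Day = 7 × week + 1. Week 8 is 7 × 8 + 1 = Day 57, and Week 12 is 7 × 12 + 1 = Day 85. The final visit is Week 12, so it is not.

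**2. What do the other schedules do?** Day named in footnote c against the part's final visit:

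| Part | Tables | Day in footnote c | Final visit |
|---|---|---|---|
| SAD | 2, 13 | 57 | 57 |
| Single dose expansion | 3, 14 | 57 | 85 |
| Multiple ascending dose (MAD) | 4, 15 | 85 | 85 |
| Multiple dose expansion | 5, 16 | 113 | 113 |

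Six of the eight footnotes name their own part's final day. Only Tables 3 and 14 do not. The pattern suggests the meaning: the scheduled final day, or the EOS visit if the subject leaves early.

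**3. Days missed if a site stops at Day 57.** Dosing is on Day 1 and visits are taken at their nominal days. Days missed = end day − 57. Post-dose days = end day − 1.

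| End day taken as correct | Source | Days missed | Post-dose days | Share |
|---|---|---|---|---|
| 85 | EOS visit; Protocol 9.5.1 | 85 − 57 = 28 | 84 | 33.3% |
| 85 + 7 = 92 | SAP 6.9.1 | 92 − 57 = 35 | 91 | 38.5% |
| 85 + 14 = 99 | Protocol 7.3.1 | 99 − 57 = 42 | 98 | 42.9% |

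**4. Days missed if a site acts on the EOS alternative.** 85 − 85 = 0 days up to the EOS visit.

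**5. What remains once the footnote says Day 85.** The gap to the EOS visit is 0. The SAP's last day is still 92 − 85 = 7 days beyond the footnote, and the end in Section 7.3.1 is 99 − 85 = 14 days beyond it. Events on Days 86 to 92 would be counted by the SAP but lie outside the Protocol's treatment-emergent definition. Events on Days 93 to 99 would be collected under Section 7.3.1 but fall outside the SAP window.

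**6. Subjects exposed.** At most 39 if three groups are selected (3 × 13), about 26 if two are (2 × 13), and none if this part does not open.

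**The case against.** A reader might infer that the schedule stops adverse event collection at Day 57 and that a third of the primary safety follow-up is therefore lost. The documents do not support that.

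- The phrase offers EOS as an alternative, and EOS here is Day 85.
- The grid to which the footnote belongs marks an adverse event assessment at Week 12, so a site working from the table is told to ask about events at that visit.
- The footnote goes on to deal with events ongoing at Day 85 and calls for assessment at least monthly.
- Section 7.3.1, the treatment-emergent definition and the SAP all run to Day 85 or later. Section 7.3.3 requires the sponsor to be told of possibly related events learned of even after the collection period.
- Two of the four primary safety endpoints, bone conduction audiometry and the tinnitus scale, are scheduled at Day 85 whatever footnote c says.

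Nor should the 42 days to Day 99 be charged to this error. Fourteen of them come from the separate gap between every schedule footnote and Section 7.3.1.

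All of this stands, and it makes the 33% a worst case. It does not remove the defect. In the other schedules the named day is the scheduled final day, so on the same pattern these two tables point a completing subject's site to Day 57, and footnote c contradicts itself from one sentence to the next.

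**Conclusion.** The inconsistency is real and stands in the current text of two tables. It is best described as an apparent carry-over from the SAD footnote, not a design decision. Its effect on collection up to the EOS visit ranges from 0 days, where a site acts on the EOS alternative or the Week 12 mark, to 28 of 84 post-dose days (33%), where a site follows the literal Day 57. The documents do not show how sites would read it. Only treatment-emergent events and events of special interest are affected, and only if single dose expansion opens.

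The footnote also exposes a wider disagreement. For this one part the documents give Day 57 (or EOS), Day 85, Day 92 and Day 99 as the end of the adverse event period. These figures assume that the last visit falls on its nominal day. The correction is worth making because the endpoints are primary and the change is small.

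**What to change.** 1. In Protocol Tables 3 and 14, change footnote c to Day 85 or EOS, matching the pattern of the other six schedule footnotes.
2. Reconcile the end of adverse event collection across the schedule footnotes (final day or EOS), Protocol Section 7.3.1 (last visit + 14 days), the treatment-emergent definition in Protocol Section 9.5.1 (EOS visit) and SAP Section 6.9.1 (the earlier of the EOS day and Day 85, + 7 days). State one collection period and one counting window, with collection lasting at least as long as the window.

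Adding the 14 days to every footnote would not be enough on its own, because Section 9.5.1 and the SAP would still end on different days.

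The cost is a few lines in a protocol amendment and, if the counting window changes, a matching edit to the SAP before database lock. No visit, procedure or sample size changes.
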